Internal ref. no. (or short title)	MIDNIGHT Trial				
Clinical Phase	Phase 2				
Trial Design	Randomised, double blind, pla	acebo controlled, cross over			
Trial Participants	Intensive care unit medical ar	nd nursing staff			
Planned Sample Size	32				
Treatment duration	3 nights x 2 occasions				
Follow up duration	End of final study visit				
Planned Trial Period	3 years				
	Objectives Outcome Measures				
Primary	To determine the feasibility of a trial of Circadin vs placebo in medical and nursing staff working nightshifts on the intensive care unit.	Recruitment and randomisation of 25 individuals completing both arms of the crossover design.			
Secondary	Determine effect of night shift working on transcriptome.	Differential gene expression between baseline and end of shift on Day 1, and end of shifts series on Day 4.			
	Determine effect of Circadin on transcriptome.	Differential gene expression between placebo and active arms on Day 4.			
	Determine effect of night shift working on cytokine profile.	Serum IL-6 and TNF α levels at baseline, end of shift on Day 1 and on Day 4.			
	Determine effect of Circadin on cytokine profile	Serum IL-6 and TNF α levels after placebo and active arms on Day 4.			
	Determine metabolism of Circadin	Serum melatonin and 6- hydroxymelatonin sulphate levels at each time point			
	Determine effect of Circadin on sleep measures	Verran and Snyder-Halpern sleep scale, Epworth sleepiness scale, data from wristband activity monitor			

	Determine effect of Circadin on psychomotor function Determine whether usual sleep habits impact on effect of Circadin	Psychomotor vigilance task, double digit addition test. Usual sleep habits and owl- lark questionnaires.		
	trial.	focus group.		
Intervention	Circadin [™] or matching placebo			
Formulation, Dose, Route of Administration	Oral, 6mg, modified release tablets			

FUNDING AND SUPPORT IN KIND

FUNDER(S) (Names and contact details of ALL organisations providing funding and/or support in kind for this trial)	FINANCIAL AND NON FINANCIAL SUPPORT GIVEN
British Journal of Anaesthesia/Royal College of Anaesthetists	Financial support for the study.
Flynn Pharma	Provision of Circadin and matching placebo, free of charge.

ROLE OF STUDY SPONSOR AND FUNDER

EMEA	European Medicines Agency
ESS	Epworth Sleepiness Scale
EU	European Union
EUCTD	European Clinical Trials Directive
EudraCT	European Clinical Trials Database
EudraVIGILANCE	European database for Pharmacovigilance
GCP	Good Clinical Practice
GMP	Good Manufacturing Practice
IB	Investigator Brochure
ICF	Informed Consent Form
ICH	International Conference on Harmonisation of technical requirements for registration of pharmaceuticals for human use.
IL	Interleukin
IMP	Investigational Medicinal Product
IMPD	Investigational Medicinal Product Dossier
ISF	Investigator Site File
ISRCTN	International Standard Randomised Controlled Trials Number
МА	Marketing Authorisation
MHRA	Medicines and Healthcare products Regulatory Agency
MS	Member State
NHS R&D	National Health Service Research & Development

PC-PVT	Psychomotor Vigilance Test
PI	Principal Investigator
PIS	Participant Information Sheet
QA	Quality Assurance
QC	Quality Control
RCT	Randomised Control Trial
REC	Research Ethics Committee
REM	Rapid Eye Movement
SAE	Serious Adverse Event
SAR	Serious Adverse Reaction
SDV	Source Data Verification
SOP	Standard Operating Procedure
SmPC	Summary of Product Characteristics
SSI	Site Specific Information
SUSAR	Suspected Unexpected Serious Adverse Reaction
TMG	Trial Management Group
TNF	Tumour Necrosis Factor
TSC	Trial Steering Committee
TMF	Trial Master File
VSH	Verran and Snyder-Halpern (Sleep Scale)

STUDY PROTOCOL

Melatonin in doctors and nurses working nightshifts- MIDNIGHT Trial

1 BACKGROUND

Circadian rhythm is controlled by cells located in the suprachiasmatic nucleus (SCN) which receive information about the level of illumination from the eyes and feed this information to the pineal gland which secretes the hormone melatonin. During daytime, circulating melatonin concentrations are very low. The start of melatonin secretion, 'dim light melatonin onset' (DLMO) is ~2h before sleep onset, peaking around 4am, and coinciding with low body temperature and alertness [1]. In night shift workers, until the DLMO has altered and sleeping is 'in phase' with melatonin to night shifts usually takes around 1 day for each hour of change, but some night shift workers never adapt [4]. An ICU presents a highly demanding workplace and failure to cope with adaptation to irregular night working may impact on patient safety [5]. A very recent study reported sleepiness and fatigue during night shifts in ICU nurses, coupled with increased response times and decreased mathematical problem solving productivity [6].

Around 10% of genes are controlled by circadian rhythm and there are gene transcript changes in the blood of human volunteers after sleep deprivation [7] or when sleep is out of phase with melatonin secretion [8]. Shift work involving circadian disruption is associated with increased risk of cancer [9,10] and other adverse health outcomes such as mental health issues [11], cardiovascular disease [12,13] and reproductive problems [14] have been reported. It has been suggested that melatonin may promote beneficial pathways [15-17]. Although studies of changes in immune function in shift workers are less clear [18] it is well known that sleep deprivation results in changes in cytokines particularly interleukin-1 (IL-1) and tumour necrosis factor (TNF) α [19-23]. Melatonin affects genes, epigenetic processes and transcriptional activators which regulate cytokine responses and this may modulate the changes induced by sleep deprivation [21,24,25].

Poorer cognitive performance has been reported during night shifts compared to day shifts [26,27]. Exogenous melatonin was 'remarkably effective' in preventing or reducing 'jet lag' [26] but effects on sleep were less clear [29,30]. In night shift workers, melatonin was beneficial in some studies [31-33]. The effect of exogenous melatonin on either cognitive function or the human transcriptome has not been reported in night shift workers. ICU nurses were recently reported to improve their ability to adapt to night shifts in part by napping during night shifts, which is concerning [6].

At Aberdeen Royal Infirmary, trainee doctors work 4 consecutive nights at approximately 6 week intervals and nurses work 7 consecutive nights at 4 week intervals. We hypothesise that exogenous melatonin may be beneficial at a molecular/physiological level. The aim of this study is to investigate the effects of exogenous melatonin compared to placebo in medical and nursing staff working night shifts. We will assess affects on sleeping patterns, psychomotor vigilance and biochemical measures and effects on the transcriptome will be determined. We will assess, in a double blinded randomised controlled cross-over pilot study, whether nightly doses of oral melatonin are able to improve sleep and psychomotor vigilance and modify gene transcripts and cytokines.

2 RATIONALE

Poorer cognitive performance and increased time to undertake tasks have been reported in people working night shifts, compared to day shifts. Adaptation to night shifts requires sleeping patterns and endogenous melatonin secretion to be 'in phase'. Melatonin has effects

on genes, and changes to the human transcriptome in healthy subjects when their sleep pattern is out of phase with melatonin secretion has been reported. There are no reports of the effects of exogenous melatonin on transcripts in night shift workers. The aim of this pilot study is to determine the effects of exogenous melatonin administration compared with placebo in medical and nursing staff working night shifts. This pragmatic pilot study will assess, in a double blinded randomised cross-over trial, whether melatonin given before sleep time can improve sleep and psychomotor vigilance and modulate transcript changes. In the placebo phase we will be able to determine if the transcriptome changes described when sleep is out of phase with melatonin secretion are also seen in actual night shift workers. Changes in gene transcripts may explain the health disadvantages of shift working and melatonin may be a useful intervention.

2.1 Assessment and management of risk

There is no evidence of risk of melatonin administration even at very high doses from very many studies in both healthy people and disease conditions. The potential benefit to the individual participant is limited to the possibility of improved sleep cycle during one of the night shifts.

This trial is categorised by the MHRA as **not** being a Clinical Trial of an Investigational Medical Product (CTIMP).

The study represents use of a licensed product with an established safety profile in a subject population outside of that licence and indication but not for a clinical condition. The safety and efficacy of melatonin has been studied in populations of similar age to those we are studying (>18 years) and in paediatric populations (to manage sleep disturbance in children with neurodevelopmental disorders).

3 OBJECTIVES AND OUTCOME MEASURES/ENDPOINTS

The aim of this pilot study is to investigate the feasibility of this trial design to assess the effects of exogenous melatonin (Circadin) compared to placebo in medical and nursing staff working night shifts and the most appropriate endpoint measures for future studies. This is a pilot study- there are no previous data on which to base a sample size calculation. We will explore effects of Circadin on sleeping patterns, psychomotor vigilance and biochemical measures and on the transcriptome. The various measures of sleep will include quality, latency, disturbance, and sleepiness. Psychomotor function will be assessed using reaction time testing and double digit addition tasks. Cytokine profiles, melatonin and 6-hydroxymelatonin concentrations and gene transcripts will be measured. Since much of previous data have not been reported in people actually working night shifts, this study will generate important data even in the absence of any effect of Circadin, which is unlikely.

3.1 Primary objective

The primary objective is to undertake a pilot feasibility trial of 6mg slow release melatonin (CircadinTM) before sleep periods compared to placebo in medical and nursing staff working night shifts at Aberdeen Royal Infirmary. The study is a pilot study with no formal sample size calculation.

3.2 Secondary objectives

The secondary objectives are to:

- Determine effect of night shift working on the transcriptome.
- Determine effect of Circadin on the transcriptome.
- Determine effect of night shift working on the cytokine profile.
- Determine effect of Circadin on the cytokine profile.

- Determine metabolism of Circadin.
- Determine effect of Circadin on sleep measures.
- Determine effect of Circadin on psychomotor function.
- Determine whether usual sleep habits impact effect of Circadin
- Determine participants' views about the trial.

3.3 Primary endpoint/outcome

The primary endpoint is successful completion of the trial, defined as recruitment, randomisation and protocol completion of 25 individuals ie both arms of the crossover design. We aim to recruit 32 subjects to account for dropout and non-completion.

3.5 Secondary endpoints/outcomes

Objectives	Outcome Measures	Timepoint(s) of evaluation of this outcome measure (if applicable)				
Primary Objective	Randomisation of 32 subjects with the aim of 25 completing both arms of the crossover design. This will allow for at least 20% attrition rate which is fairly standard in such studies.					
Secondary Objectives	Determination of drop out, non completion and retention rate	Trial end.				
	Differential gene expression	and end of shifts series on Day 4.				
	Differential gene expression between placebo and active arms.	Blood samples Day 4 after each shift series.				
	Serum IL-6 and TNF α levels.	Blood samples on Day 1, and end of shifts series on Day 4 .				
	Serum IL-6 and TNF α levels after placebo and active arms.	Blood samples Day 4 after each shift series.				
	Serum melatonin and 6- hydroxymelatonin sulphate levels at each time point	Blood samples on Day 1 before shift, and end of each shift for shift series.				
	Verran and Snyder-Halpern sleep scale, Epworth sleepiness scale, data from wristhand activity monitor	VSH before each shift. ESS before, during and after each shift. Activity monitoring during each sleep period.				
	Psychomotor vigilance task, double digit addition test	PVT and DDAT before and after each shift				
	Usual sleep habits and owl-lark questionnaires.	Before randomisation.				
	Questionnaire about trial.	Trial end.				
	Focus group on trial.	Trial end (requires additional consent)				

*Additional consent will be obtained

Figure 1

Summary of the trial design.

4 TRIAL DESIGN

This is a randomised, double blind, placebo controlled crossover pilot study. See Figure 1 and Table 1.

5 STUDY SETTING

This is a single centre study and will recruit staff working within Aberdeen Royal Infirmary, NHS Grampian. Doctors and nurses who routinely undertake periods of night shift working will be recruited by advertisement and global emails from a third party. Some parts of the study will be completed within the volunteers' home setting – eg questionnaire completion.

6 ELIGIBILITY CRITERIA

Following written informed consent, 32 participants of either sex, non-smokers, not taking regular medicine and with no health complaints will be eligible. Exclusion criteria will be pregnancy, breastfeeding, *ad hoc* use of sedatives, and known allergy to drug contents. Anyone with pre-existing health problems will not be recruited. A simple screening questionnaire will be used prior to recruitment (Appendix 4).

6.1 Inclusion criteria

Any male or female member of staff working nightshifts to a regular pattern and who can commit to both arms of the study ie 2 series of night shifts approximately 4-6 weeks apart, will be eligible.

6.2 Exclusion criteria

We will only recruit subjects who do not have a body mass index within the obese or overtly underweight range and who do not have self reported sleeping issues before the study starts. Other exclusion criteria include pregnancy (or trying to get pregnant- female participants), breast feeding, current use of sedatives, hypnotics, anti-histamines and herbal sleep remedies and known allergy to drug contents. Female subjects will be asked to confirm that they are not trying to get pregnant and that they one of the following apply: using adequate contraception and will continue to do so for the duration of the trial, or that they have been sterilised, or they are post-menopausal, not sexually active, or infertile (see Appendix 4).

7 TRIAL PROCEDURES

The study design is summarised in Figure 1 and the timing of tasks, questionnaires and samples are shown in Table 1. The burden of tasks and questionnaires have been considered with regards to burden and fatigue.

7.1 Recruitment

The study will be advertised to volunteers by global emails and posters. Volunteers will make themselves known to any of the trial investigators. They will then be given a copy of the participant information sheet and if they wish to take part after the study is explained to them they will be asked to sign a consent form. Consent can be obtained from any delegated member of the research team who has undergone GCP and taking consent training.

7.1.1 Screening

Before the study, subjects will provide basic demographic information (Appendix 4). Anyone who has a chronic health issue, or fulfils any of the other exclusion criteria will not be recruited.

7.2 Consent

The Chief Investigator (CI) retains overall responsibility for the informed consent of participants but a delegated member of the research team will also be able to take informed consent. The right of a participant to refuse participation without giving reasons will be respected and participants remain free to withdraw at any time from the trial without being

obliged to give reasons. However we will record a reason if offered one since this is valuable information for a feasibility study such as this. Once recruited, each subject will be assigned a unique ID number and any identifiable information will be kept securely in a locked office to which only the chief investigator has access.

7.2.1 Additional consent provision for collection and use of participant data and biological specimens in ancillary studies

Any biological samples remaining will be stored in a biobank, pending use in further related research, subject to any ethical requirements. Samples will be anonymised with a unique identification number. Participants will be asked to consent to such storage; those who choose not to consent to this will still be eligible to take part but their samples will not be placed into the biobank. We will also request consent from subjects to be contacted after the trial is complete to ask about taking part in a focus group to find out participants' views about the trial.

7.3 Randomisation scheme

Volunteers will be randomized to receive either placebo or melatonin and will then receive the opposite during the next study intervention. As such they will be acting as their own controls. Randomisation will be by random number provided by a third party not involved in the trial, in blocks of 8 such that for each 8 subjects randomised, four will receive melatonin first and 4 will receive placebo first. This block allocation will ensure that within a close time window (within 4-6 weeks) to minimise seasonal effects. The schedule will be provided to the Clinical Trials Pharmacy in advance.

7.3.1 Method of implementing the allocation sequence

Study drug or an identical placebo will be dispensed from pharmacy by the research pharmacist according to a previously supplied randomisation code list. This will be prepared by an independent statistician.

7.4 Blinding

Researchers and volunteers will be blinded at all times to the treatment allocation. Placebo and melatonin will be tablets of identical appearance. Blinding will be maintained unless it is considered necessary to unblind for safety reasons. This can be rapidly achieved by contacting Pharmacy.

7.5 Unblinding

The code breaks for the trial will be held in the clinical trials pharmacy. In the event that unblinding is required then a formal request for unblinding will be made by the CI. Should unblinding be required then the information will be disseminated to the Data Monitoring Committee (DMC) for review in accordance with the DMC Charter.

7.6 Baseline data

Questionnaires to record usual sleeping habits will be completed. We will use the usual sleep habits questionnaire (Appendix 5), the Composite Scale of Morningness (CSM), also known as the owl and larks questionnaire (Appendix 6) [37-41], and the Verran and Snyder-Halpern (VSH) sleep scale (Appendix 7) [34,42,43] to provide some baseline information. CSM scores have been found to correlate with self-reported alertness, rising times and retiring times across various cultures. This will be done once before the first night shift and will relate to usual habits when not working night shifts.

7.7 Trial assessments

Immediately before the first shift subjects will have a baseline blood sample taken and will complete the Epworth Sleepiness Scale (ESS) and the VSH sleep scale [34,42,43]. A baseline personal computer based psychomotor vigilance task (PC-PVT) will be undertaken [44,45]. A double digit addition test (DDAT) will also be used to test problem solving performance, where subjects have to repeatedly add two random double-digit numbers together for a period of 5 minutes (example given in Appendix 8). The percentage of correct answers and the time taken to undertake each addition, plus any lapses, defined as a response time of more than 10s, will be recorded. The worksheet for this is created online and a different sheet will be used each time: http://www.math-aids.com/Addition/Addition_Drills.html.

The ESS will be repeated mid-way through the shift. At the end of the shift, subjects will have another blood sample taken and undertake the PC-PVT and the ESS again before going home, where they will take 6mg melatonin (as Circadin) or a matching placebo with a small snack before going to bed. The means and duration of travel home and the time of dosing and bedtime will be recorded. Subjects will wear a wristwatch style activity monitor during the sleep period, which records activity, sleep and restlessness, REM sleep duration, body temperature and heart rate data that can be downloaded for subsequent analysis.

Subjects will be asked to wear sunglasses on their journey home if it is light. Subjects will be asked not to attempt to sleep during the day before starting the first night shift and to go to bed as soon as possible when they get home after the shift has ended. They will be asked not to nap during the shift. They will also be asked to refrain from consuming acohol whilst study visits are ongoing. The VSH sleep scale and ESS will be completed again at home when they wake. All PC-PVT tests will be undertaken with a researcher present; the mid-shift ESS will be completed by the subject but a text message reminder will be sent to aid compliance. On each of the next 2 subsequent shifts subjects will undertake the same processes. Around 4-6 weeks later when subjects work another series of night shifts, they will go through the same procedure, but take melatonin if they previously took placebo, and vice versa. Consideration has been given the number of tasks and questionnaires at any one time point to minimise burden and inconvenience such that the time requirement will be no more than 15 minutes in total at any time point.

Biochemical assays

Serum melatonin will be measured using liquid chromatography-tandem mass spectrometry, a method which we have developed in-house. The major metabolite of melatonin, 6-hydroxymelatonin, will be measured in serum as the sulphated form in serum using enzyme immunoassay. Biochemical tests will include urea and electrolytes, liver function tests and differential leucocyte counts. Cytokines (IL-1/6 and TNF α) will be measured using high sensitivity immunoassays. Changes in melatonin/6-hydroxymelatonin and cytokines between melatonin and placebo and between shifts will be determined.

Psychomotor vigilance testing and addition testing

The PC-PVT requires sustained attention and measures how subjects respond to a visual stimulus- a light comes on randomly every few seconds for 5–10 minutes and subjects click as soon as the light appears. In addition to reaction time we will also record when the mouse is not clicked when the light comes on, thus counting the number of lapses in attention of the subject. The PVT does not allow learning and is unaffected by individual aptitude. The software is freely available to download and incorporates data analysis capability. A two digit addition test will also be used to test problem solving performance, where subjects have to repeatedly add two random double-digit numbers together for a period of 5 minutes. The percentage of correct answers and the time taken to undertake each addition, plus any lapses, defined as a response time of more than 10s, will be recorded.

Sleep scales/questionnaires

The VSH sleep scale is a validated scale which uses 100mm visual analogue scales to record sleep disturbance, efficiency and supplementation. This will be used to assess how subjects slept the night before the study, then after each night shift to compare quantitative data between placebo and melatonin and between shifts. The ESS which assesses 'sleepiness' and the CMS questionnaires will provide semi-quantitative/descriptive information.

Wristband activity/sleep monitor

These unobtrusive devices were designed for activity or fitness monitoring but can also be used to record periods of sleep, including REM sleep (via movement, heart rate and body temperature), and any restlessness. Subjects will be asked to wear one of these during the sleeping period after each shift. Data can then be downloaded to an online application for analysis. There are several models available with effective sleep analysis capability.

Transcriptome analysis

Blood samples will be taken from all subjects for transcriptome analysis during each series of shifts as follows: 1. Before the first shift (baseline, 'in phase'). 2. Before the second shift (completely 'out of phase'). 3. Before the fourth shift ('beginning to readjust'). Total RNA will be isolated from all samples using the Paxgene system which produces samples which are stable for many months.

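### The vigilance-test lapse is a missed click with no time limit, so slow but completed responses are left out and the count may be sparse

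*Protocol*

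**What the plan says.** Section 7.7, under psychomotor vigilance and addition testing, describes the PC-PVT as a task in which "a light comes on randomly every few seconds for 5–10 minutes and subjects click as soon as the light appears". It then gives two outputs. The first is reaction time. The second is a tally of stimuli that draw no response, and the sentence ends "clicked when the light comes on, thus counting the number of lapses in attention of the subject", with the negative standing just before the quoted words. A PC-PVT lapse is thus a light that receives no click. The protocol does not say how long the light stays on, or how late a click may come before the stimulus counts as missed.

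For the addition test the same section uses a timed rule: "plus any lapses, defined as a response time of more than 10s, will be recorded".

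On scoring, the protocol adds only that "The software is freely available to download and incorporates data analysis capability". It does not describe the software's own lapse rule.

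Section 3.5 schedules "PVT and DDAT before and after each shift", and Table 1 adds a test before the fourth shift. The Background (section 1) describes sleepiness and fatigue in ICU nurses on night shifts, "coupled with increased response times and decreased mathematical problem solving productivity".

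**The concern.** The two tests in section 7.7 use different ideas of a lapse, and no reason is given. One rule is a time limit and the other is complete absence of a response. The deficit the protocol expects at night is slowing. A participant who notices the light late and then clicks shows that slowing, yet adds nothing to the PC-PVT lapse count.

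The rule is also incomplete. Without a response window, a very late click could be scored as a miss or as an ordinary response, depending on a setting the protocol does not state.

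Section 3 says the pilot should help to identify suitable endpoint measures for later studies, and section 10.1 says it should allow a formal sample size calculation for a definitive trial. If most tests return a lapse count of zero, the count gives little information on variance or effect size. A reader could then set lapses aside as an endpoint because of the scoring rule and not because of the participants' behaviour.

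**Working it through.** **The plan's own figures.** The protocol states no lapse rate, effect size or variance for the PC-PVT, so there is no lapse figure to reproduce. The only related figure is the sample size. With 25 completers and 20% attrition (section 3.5), 25 / 0.80 = 31.25, which rounds up to the stated 32. The check below uses the 25 completers.

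**Inputs**
- Stimuli per test: section 7.7 gives 5 to 10 minutes and a light every few seconds. Assuming a mean gap of 3 to 10 s, the range is 5 × 60 / 10 = 30 to 10 × 60 / 3 = 200. The central case is 100.
- Tests after the first dose, per series: 5 (before and after shifts two and three, and before shift four; section 3.5 and Table 1).
- Missed-click rate p: not in the protocol, so varied from 0.01% to 5% of stimuli as an assumption.

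**Share of tests with no lapse.** If every stimulus is missed independently with probability p, P(zero) = (1 − p)^stimuli. For example, 0.999^100 = 0.905 and 0.99^100 = 0.366.

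**Expected lapses per arm.** p × stimuli × 5 × 25. At p = 0.1% and 100 stimuli this is 0.001 × 100 × 5 × 25 = 12.5 over the whole arm.

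**Power for a halving of the count.** Simulated with 25 pairs, Poisson counts over 5 tests per arm, between-person coefficient of variation 1, a Wilcoxon signed-rank test at two-sided 0.05, and 1,000 replicates per case. The trial is not powered for this comparison. The figure only shows how informative the count would be.

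| Stimuli per test | Assumed miss rate | Tests at zero | Power for a halving |
|---|---|---|---|
| 30 | 0.1% | 97% | 2% |
| 30 | 1% | 74% | 62% |
| 30 | 5% | 21% | 99% |
| 100 | 0.01% | 99% | about 0% |
| 100 | 0.1% | 90% | 24% |
| 100 | 0.5% | 61% | 83% |
| 100 | 1% | 37% | 97% |
| 200 | 0.1% | 82% | 44% |

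The zero shares assume one common miss rate. If people differ as in the simulation (gamma with coefficient of variation 1), the share is 1 / (1 + m), where m is the mean count per test. For 100 stimuli that is 1 / 1.1 = 91% at 0.1% and 1 / 2 = 50% at 1%, so the zeros are somewhat more common.

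**What a timed rule would add.** Counting late responses together with non-responses includes every missed click, so the count cannot be smaller. As an illustration, take lognormal reaction times and a 500 ms threshold, all assumed:
- Median 280 ms, log-SD 0.25, 50 stimuli: z = ln(500/280) / 0.25 = 2.32, tail 0.010, about 0.5 late responses per test.
- Median 380 ms, log-SD 0.35, 100 stimuli: z = ln(500/380) / 0.35 = 0.78, tail 0.217, about 21.7 late responses per test.

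The same curve should not be used to estimate missed clicks. It has no separate process for inattention or brief sleep, so it makes misses rare by construction.

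**The case against.** The strongest reply is that lapses are an addition and reaction time is the named measure. Section 3 says psychomotor function is assessed by reaction time testing and addition tasks, section 10.3.1 treats the vigilance task as continuous, and the outcome lists name no lapse endpoint. Late responses stay in the data as long reaction times, and a timed count can be derived from them later. All of this stands, and it limits the reach of the point.

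A second reply is that the software's own analysis, or a statistical analysis plan that is not shown, may set the scoring rule. That is possible. However, section 7.7 does more than leave the rule open. It says what is counted as a lapse, and a later plan that followed it would inherit the missed-click rule.

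A reader might go further and infer that missed clicks are almost never seen in awake staff, that the count will sit at zero in both arms, and that it cannot show an effect. The protocol does not support this. Each step needs a missed-click rate, and none is given. In the table, the count is close to useless at 0.01% of stimuli and quite informative at 1%. A reader might also infer that lapse information is thrown away. It is not, because the reaction times are recorded.

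**Conclusion.** The point holds in a limited form. As written, the PC-PVT lapse is a missed click without a threshold or window, it differs in kind from the addition-test lapse, and it leaves out the slow responses that the protocol itself names as the night-shift problem.

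A sparse count is a real risk but not a certainty. At 100 stimuli per test, a miss rate of about 1 in 1,000 or lower leaves at least 90% of tests at zero. At 1 in 100 the share is 37%. Both figures rest on assumed rates and an assumed number of stimuli.

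The consequence is confined to one exploratory secondary variable in a feasibility pilot. The primary endpoint of 25 completers and the reaction-time results are unaffected. The change is a free improvement.

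**What to change.** In section 7.7, define a PC-PVT lapse before any data are seen as a reaction time above a prespecified threshold, or no response within a stated window. A threshold of 500 ms would serve as an example, but it is an assumption and is not taken from the protocol. The investigators should choose the value and state the reason for it. Derive the count from the reaction times already recorded, and report true non-responses as a separate count.

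The cost is a sentence or two in section 7.7. No new test, visit or data item is needed. Setting the threshold in advance matters because one chosen after the results are known would be a weaker basis for planning the later trial.
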